# PROTOCOL VERSION HISTORY

Version No	Date	Change in protocol	Reason
Version 1.0	11-MAR-2022	Yes	For clarification on colonoscopy requirement
Version 2.0	17-OCT-2023	No	

# Summary of Changes from Version 1.0 dated 11-MAR-2022 to Version 2.0 dated 17-OCT-2023

Sl. No	Section(s) changed in the protocol version 1.0 dated 11-MAR-2022	Initial statement	Proposed change	Reason for change	Anticipated impact, if any
1	Exclusion criteria no.2	Subject of any age with evidence of clinically significant weight loss, anemia, or rectal bleeding and without documentation of the results of either a flexible sigmoidoscopy or colonoscopy performed within 2 years period prior to screening.	Subject of any age with evidence of clinically significant weight loss, anemia, or rectal bleeding and without documentation of the results of either a flexible sigmoidoscopy or colonoscopy performed within 2 years period prior to screening.  Note: Colonoscopy can be avoided for patients age less than 45 years and those who do not have alarming symptoms of weight loss, rectal bleeding or anemia in past 6 months based on Investigator discretion/ Medical Monitor opinion.	Clarification on colonoscopy requirement	None
2	Section 4.1(Overview of the Study Design-Treatment period).	Patient will be advised to take study drug once daily in the morning at least 30 minutes before breakfast from Day 1.	Patient will be advised to take study drug once daily in the morning before breakfast from Day 1.	Typographical error	None
3	Appendix 2 (Study personnel): Sponsor contact	[name] Lead —Clinical Operation and Strategy [name] Ltd. Email ID:[name] [contact]	[name] Head Clinical Development & Clinical Strategy [name] Ltd. Email ID: [name]	Administrative change	None

[figure not shown]

# PROTOCOL SYNOPSIS

Title of study	A randomized, multicentre, double blind, placebo
	controlled, parallel-group study to evaluate the
	efficacy and safety of Elobixibat once daily of Dr.
	Reddy's laboratories limited in patients with chronic
	constipation.
Protocol ID	DRL-IND-NDA03-ELO/2022
Sponsor	[name] Limited
Phase of Study	Phase III
Study rationale in brief	Constipation is defined by bowel disturbances (i.e.,
	reduced frequency of bowel habits, hard stools,
	excessive straining to defecate, a sense of anorectal
	blockage, anal digitation, and a sense of incomplete
	evacuation after defecation).
	Chronic constipation (CC) is common among the
	elderly population. Many challenges are associated
	with the diagnosis and management of patients with
	CC. Some of these challenges arise from the current
	incomplete understanding of what causes constipation
	and from the difficulties in diagnosing and classifying
	the heterogeneous group of patients with CC.
	Constipation is labelled as 'Chronic idiopathic
	constipation (CIC)' when the cause cannot be
	identified. Global prevalence of CIC is 20%.
	Population based study from India in 505 people
	found the prevalence of constipation by the Rome II
	criteria to be 16.8% and self-reported constipation to
	be 24.8% in the last 1 year.

Despite the availability of different treatment options for constipation, an unmet need for drugs in the treatment of patients with CC remains. A subset of patients with CC have reduced fecal (and by inference, intra-colonic) bile acids (BA).

Elobixibat represents a new class of treatment for CC with a unique MOA. It is a locally-acting ileal bile acid transporter (IBAT) inhibitor, a protein that regulates reabsorption of BA. This increases the delivery of BA delivery to the colon thereby enhancing natural defecation.

Inhibition of ileal BA absorption also up regulates hepatic synthesis of BA from cholesterol, which enters into hepatocytes as LDL by binding to LDL receptors on the hepatocyte cell surface. Up regulation of hepatic BA synthesis promotes maintenance of BA pool size and may also lower serum LDL cholesterol concentrations.

Elobixibat showed accelerated colonic transit, looser stool consistency, decreased constipation rating, and reduced straining compared with placebo in a Phase IIa study over 14 days. Elobixibat was associated with a significantly greater increase in the number of SBMs (spontaneous bowel movements) per week from baseline to placebo. Elobixibat also improves bloating severity.

This study is planned to evaluate the efficacy, and safety of Elobixibat tablet (10 mg oral once daily administered as two tablets of 5 mg) in patients with chronic constipation once daily for one week and then

	dose titration (up or down) will be done according to the patient's response.
Investigational Medicinal Product	Elobixibat 5 mg tablet
Comparative	Placebo matching Elobixibat 5 mg tablet
Medicinal Product	
Study Type	Interventional
Study Design	Prospective, multicenter, randomized, double blind, parallel group, placebo controlled, phase III superiority study
Primary Objective	To evaluate the efficacy of Elobixibat tablet in patients with chronic constipation.
Secondary Objective	To evaluate the safety and tolerability of Elobixibat tablet in patients with chronic constipation.
Sample size calculation	A total of 150 Patients with chronic constipation.  Assuming a significance level of 2.5% and a power of 95%, we require 60 completed subjects per treatment group (a total of 120 subjects in study) to prove superiority of Elobixibat over Placebo.  Assuming ~20% drop-out rates, 150 subjects will be randomized in this study with 1:1 ratio (75 subjects per each arm) to Elobixibat 5mg vs Placebo.
Subjects/clinical	Male and non-pregnant female subjects (18-65 years
condition/therapeutic area	of age) with clinical diagnosis of chronic constipation will be included in the trial.
Key Inclusion Criteria	Subjects will be enrolled in the study if they meet all the following criteria.  1. Male or female patients of 18-65 years age

- 2. Ambulatory patients with chronic constipation (fulfilling Rome IV criteria) reporting <3 Spontaneous Bowel Movements (SBM) per week and reports one or more of the following symptoms for the last 3 months with symptom onset at least 6 months before the Screening Visit or before starting chronic therapy with any laxative:
- Straining during more than 25% of defecations
- Lumpy or hard stools more than 25% of defecations
- Sensation of incomplete evacuation more than 25% of defecations
- 3. Patients with less than 3 SBM per week during pretreatment period.
- 4. Willing to comply with protocol requirements and sign a statement of informed consent
- Willing to discontinue any laxatives used before the Pretreatment period in favor of the protocol-defined Rescue Medicine (bisacodyl tablets or suppositories)
- 6. Agreed to refrain from making any new, major lifestyle changes that may have affected CIC symptoms (e.g., starting a new diet or changing his or her exercise pattern) from the time of signature of the ICF to the last trial visit.
- 7. Female subjects of:

Child-bearing potential should have negative serum pregnancy test at screening and agree to use adequate birth control during the entire study period (acceptable methods include intrauterine device, barrier or abstinence).

OR

		Is surgically sterile (bilateral tubal ligation, bilateral oophorectomy, or hysterectomy has been performed on the study subject).  OR  Postmenopausal for at least 1 year
Key Exclusion Criteria		Pregnant, breast feeding, or planning a pregnancy  Subject of any age with evidence of clinically significant weight loss, anemia, or rectal bleeding and without documentation of the results of either a flexible sigmoidoscopy or colonoscopy performed within 2 years period prior to screening.
	3.	Note: Colonoscopy can be avoided for patients age less than 45 years and those who do not have alarming symptoms of weight loss, rectal bleeding or anemia in past 6 months based on Investigator discretion/Medical Monitor opinion.  Reports loose (mushy) or watery stools in the absence
		of any laxative intake in the form of a tablet, a suppository or an enema, or prohibited medicine for >25% of bowel movements.
	4.	Reported a Bristol Stool Form Scale score of 6 (loose, mushy stools) for > 1 SBM or a Bristol Stool Form Scale score of 7 (watery stools) with any SBM over the 2 weeks pretreatment period before the Randomization Visit [Refer to appendix 3 for BSFS scale] .
	5.	Received a diagnosis of inflammatory bowel disease (IBD)

6.	Meet	the	Rome	IV	criteria	for	Irritable	Bowel
	Syndr	ome	or the R	ome	IV criter	ria fo	r Opioid-l	Induced
	Const	ipatio	on as de	scrib	ed below	v:		

Rome Crit	eria for IBS and OIC
IRRITABLE BOWEL SYNDROME	OPIOID-INDUCED CONSTIPATION
Diagnostic criteria*	Diagnostic criteria
Recurrent abdominal pain on average at least 1 day/week in the last 3 months, associated with two or more of the following criteria:	New, or worsening,     symptoms of constipation     when initiating, changing, o     increasing opioid therapy,     that must include two or mo     of the following:
Related to defecation	• Straining during more than (25%) of defecations
Associated with a change in frequency of stool	• Lumpy or hard stools (Brist Stool Form Scale 1-2) more than ¼ (25%) of defecations
Associated with a change in form (appearance) of stool	
 
Sensation of incomplete evacuation more than ¼ (25%) of defecations
 
Sensation of anorectal obstruction/blockage more than ¼ (25%) of defecations
 

* Criteria fulfilled for the last 3 months with symptom onset at least 6 months prior to diagnosis	4. Manual maneuvers to facilitate more than ¼ (25% of defecations (e.g., digital evacuation, support of the pelvic floor)
	5. Fewer than three SBM per week
	6. Loose stools are rarely present without the use of laxatives.

IBS: Irritable Bowel Syndrome, OIC: Opioid Induced Constipation, SBM: Spontaneous Bowel Movement

- 7. Has a history of structural abnormality of the Gastrointestinal (GI) tract or a disease or condition that can affect GI motility.
- 8. Has a history of diverticulitis, chronic pancreatitis, active peptic ulcer disease (PUD) not adequately treated, ischaemic colitis, inflammatory bowel disease, laxative abuse, faecal impaction that required

- hospitalization or emergency treatment, pseudoobstruction, mega colon, mega rectum, bowel obstruction, descending perineum syndrome, ovarian cysts, endometriosis, solitary rectal ulcer syndrome, systemic sclerosis, pre-malignant colonic disease (e.g., familial adenomatous polyposis or hereditary non-polyposis colorectal cancer) or other forms of familial colorectal cancer.
- Diagnosis or family history of familial adenomatous polyposis, hereditary nonpolyposis colorectal cancer, or any other form of familial colorectal cancer
- 10. Current active peptic ulcer disease (i.e., disease that was not adequately treated or stable with therapy)
- 11. Has unexplained and clinically significant GI alarm signals (e.g., lower GI bleeding or heme-positive stool in the absence of known internal or external haemorrhoids, iron-deficiency anaemia, unexplained weight loss) or systemic signs of infection or colitis
- 12. Has a potential central nervous system (CNS) cause of constipation (e.g., Parkinson's disease, spinal cord injury, multiple sclerosis)
- **13**. Has intestinal/rectal prolapse or other known pelvic floor dysfunction
- 14. Commonly uses digital maneuvers (perianal pressure or digital disimpaction) or vaginal splinting to facilitate the passage of a bowel movement
- 15. Has a history of diabetic neuropathy
- 16. Bariatric surgery for treatment of obesity, or surgery to remove a segment of the GI tract at any time before the Screening Visit, surgery of the abdomen, pelvis, or

- retroperitoneal structures during the 6 months before the Screening Visit, an appendectomy or cholecystectomy during the 60 days before the Screening Visit, other major surgery during the 30 days before the Screening Visit.
- 17. Has a history of cancer with last date of proven disease activity/presence of malignancy within 5 years, except for adequately treated basal cell carcinoma of the skin, cervical dysplasia, or carcinoma in situ of the skin or the cervix
- 18. Known human immunodeficiency virus (HIV) or Hepatitis B/C (HBV/HCV) infection
- 19. Has a history of hospitalization for any psychiatric disorder, or any suicide attempt in the 2 years prior to Screening
- 20. History of alcohol or drug abuse during the 6 months prior to Screening
- 21. Reported using a Prohibited Medicine (excluding laxatives, suppositories, and enemas) during the Pretreatment Period or not willing or able to abide by the restrictions regarding use of Prohibited Medicines (Note: The use of fiber, bulk laxatives, or stool softeners [such as docusate] is acceptable provided the patient is on a stable dose during the 30 days before the Screening Visit and planned to continue on a stable dose throughout the trial).
- 22. Patients having following lab parameters deranged defined as follows:
  - Renal function: Serum Creatinine ≥1.5 × upper limit of normal (ULN)

	• Hepatic function: AST and ALT ≥3 × ULN;
	• Hemoglobin: < 8g/dL
	23. Has clinically significant laboratory findings or
	medical condition that could potentially affect study
	participation and/or personal well-being, as judged by
	the investigator.
Randomization	Subjects meeting the inclusion criteria and none of the
	exclusion criteria will be randomized to either of the
	following 2 arms.
Dosing Schedule	Test Arm: Elobixibat tablet
	The usual adult dosage is 10 mg of Elobixibat
	administered orally once daily before breakfast. The
	dose may be adjusted according to the patient's
	response, but the maximum daily dose will be 15 mg.
	Therefore, Elobixibat tablet (10 mg oral once daily
	administered as two tablets of 5 mg) in patients with
	chronic constipation once daily for one week and then
	dose titration (up or down) will be done according to
	the patient's response.
	Comparator Arm: Placebo matching test product
	Placebo tablet matching test product (10 mg oral once
	daily administered as two tablets of 5 mg) in patients
	with chronic constipation once daily for one week and
	then dose titration of placebo (up or down) will be
	done according to the patient's response.
Rescue Medicine	Rescue Medicine, dispensed to patients, is a choice of
	5-mg bisacodyl tablets or 10-mg bisacodyl
	suppositories.
	During the Pretreatment and Treatment Periods,
	patients could use Rescue Medicine when at least 72
	 

	hours had passed since their previous bowel movement or when their symptoms became intolerable.  A bowel movement will not be recorded in the analysis of efficacy if it occurs within 24 hours after the last administration of a rescue medication.  Data set prepared should include daily rescue medication used for each individual who used the rescue medication at any point during the study.
Concomitant Medication	Medications other than those mentioned in prohibited medications list will be permitted. The use of concomitant medication is based on the discretion of the Investigator. The Investigator may take the opinion of Medical Monitor to check for any probable drug interactions before taking the final decision on use of concomitant medication.  It should be clearly explained whether the medication was used prior to baseline visit, during the study, or both.
Blinding	The packaging of the test and placebo products should be similar in appearance to make differences in treatment less obvious to the subjects and to maintain adequate blinding of evaluators. Neither the subject nor the investigator should be able to identify the treatment. The containers should not be opened by the subject at the study center.
Treatment duration	2 Weeks
Visits and study procedures	Visit 1 #: Screening visit Day -28 to Day -15  # 2 weeks pretreatment period (Day -14 to Day -1) between screening and randomization

T7' '. O	D 1	• ,•	• • ,	D 0
- V/101f フ・	Rando	mization	V/1C1f	1)97/()
v 151t ∠.	Nanuo	шидаион	VISIL.	Davo

Visit 3: Week 1+ (2) Days

Visit 4: Week 2+ (2) Days/ End of Study

• If a subject experiences any AE/SAE or worsening of the existing condition he/she can visit the site for an unscheduled visit. Subjects who withdraw from the study will be requested to attend an early termination visit, where Visit 4 procedures will be performed

#### Criteria for Evaluation: Efficacy

# **Primary Endpoint:**

- 1. Change from baseline in weekly frequency of Spontaneous Bowel Movement (SBMs), Time Frame: From Baseline to 2 weeks.
- SBM is defined as the bowel movement occurring in the absence of laxative use or manual disimpaction in last 24 hours

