# **Secondary Efficacy Endpoints:**

- 1. Proportion of patients with complete spontaneous bowel movement (CSBM)
- 2. Proportion of patients with a SBM within 24 h after the first dose of study drug
- 3. Median time to first SBM
- 4. Change from baseline in Stool consistency using Bristol Stool Form Scale (BSFS)
- 5. Change from Baseline in Weekly Degree of Straining of SBMs
- 6. Change from Baseline in Weekly Abdominal Bloating Score
- 7. Change from Baseline in Weekly Abdominal Discomfort Score

#An SBM is a BM that occurs in the absence of laxative, suppository, or enema use 24 hour of the BM or the calendar day before the BM

#A CSBM is an SBM that is associated with a sense of complete evacuation.

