- 19. Has a history of hospitalization for any psychiatric disorder, or any suicide attempt in the 2 years prior to Screening
- 20. History of alcohol or drug abuse during the 6 months prior to Screening
- 21. Reported using a Prohibited Medicine (excluding laxatives, suppositories, and enemas) during the Pretreatment Period or was not willing or able to abide by the restrictions regarding use of Prohibited Medicines (Note: The use of fiber, bulk laxatives, or stool softeners [such as docusate] was acceptable provided the patient had been on a stable dose during the 30 days before the Screening Visit and planned to continue on a stable dose throughout the trial).
- 22. Patients having following lab parameters deranged defined as follows:
  - **Renal function:** Serum Creatinine  $\geq 1.5 \times$  upper limit of normal (ULN)
  - **Hepatic function:** AST and ALT  $\ge 3 \times ULN$ ;
  - **Hemoglobin:** < 8g/dL
- 23. Has a clinically significant laboratory finding or medical condition that could potentially affect study participation and/or personal well-being, as judged by the investigator.

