#### **5.4.** Rescue Medication

Rescue Medicine, dispensed to patients, is a choice of 5-mg bisacodyl Capsules or 10-mg bisacodyl suppositories.

During the Pretreatment and Treatment Periods, patients could use Rescue Medicine when at least 72 hours had passed since their previous bowel movement or when their symptoms became intolerable.

A bowel movement will not be recorded in the analysis of efficacy if it occurs within 24 hour after the last administration of a rescue medication. Data set prepared should include daily rescue medication used for each individual who used the rescue medication at any point during the study.

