## **6.3. Efficacy Variables**

#### **6.3.1.** Primary efficacy variables

- Change from baseline in weekly frequency of Spontaneous Bowel Movement (SBMs)
  - SBM is defined as bowel movement occurring in the absence of laxative use or manual disimpaction in last 24 hours
  - Change from baseline in the frequency of SBM per week.

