#### **6.3.2.** Secondary Efficacy variables

- 1. Proportion of patients with complete spontaneous bowel movement (CSBM)
  - CSBM is defined as SBM that is associated with a sense of complete evacuation.
  - A CSBM responder is defined as a patient with ≥3 CSBMs per week and an increase of ≥1 CSBM per week from Baseline.

- 2. Proportion of patients with a SBM within 24 h after the first dose of study drug
- 3. Median time to first SBM
  - SBM is defined as a bowel movement that occurred in the absence of a laxative use or manual disimpaction.
  - Baseline value for the number of SBM is defined as the average of the numbers of SBM per week for over the 2-week pretreatment Period.
- 4. Change from baseline in Stool consistency using Bristol Stool Form Scale (BSFS)
- Change from baseline in weekly Stool Consistency using BSFS score, Time
   Frame: From baseline to 2 weeks
- The stool consistency is measured using the seven-point ordinal BSFS score.
- The BSFS classifies human stool into seven types and points them accordingly:
  - o Type 1: Separate hard lumps, like nuts (hard to pass)
  - o Type 2: Sausage-shaped, but lumpy
  - o Type 3: Like a sausage but with cracks on its surface
  - o Type 4: Like a sausage or snake, smooth and soft
  - o Type 5: Soft blobs with clear cut edges (passed easily)
  - o Type 6: Fluffy pieces with ragged edges, a mushy stool
  - Type 7: Watery, no solid pieces, entirely liquid
- Types 1 and 2 indicate constipation, with 3 and 4 represents the ideal stool form (especially the latter), and 5, 6 and 7 tends towards diarrhoea.
- For a given assessment week, the weekly stool consistency is defined as the sum of non-missing stool consistency score for SBMs during that week divided by the number of non-missing stool consistency score for SBMs during that week.
- 5. Change from Baseline in Weekly Degree of Straining of SBMs
- The degree of straining is measured using the five-point ordinal scale (1=Not at all, 2=A little bit, 3=A moderate amount, 4=A great deal, and 5=An extreme amount).
- For a given assessment week, the weekly degree of straining is defined as the sum of non-missing straining score for SBMs during that week divided by the number of non-missing straining score for SBMs during that week.

- 6. Change from Baseline in Weekly Abdominal Bloating Score
- The abdominal pain score is measured using the five-point ordinal scale (1=None, 2=Mild, 3=Moderate, 4=Severe, and 5=Very severe).

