#### 8.4. Concomitant treatment

• Prohibited Medication:

Prescription and over-the-counter (OTC) laxatives other than those prescribed as a rescue medication during the baseline/washout period by the Investigator.

Note: the use of fiber, bulk laxatives, stool softeners [surfactants such as docusate], and probiotics are acceptable, provided that the patient has been on a stable dose for 30 days before the Screening Visit and plans to continue stable dosing for the duration of the trial.

- Significant change in diet.
- Over-the-counter or prescription laxatives cannot be administered during the pretreatment period(s).

All medicine listed below ("1-day Washout" and "14-day Washout") are excluded during the Pretreatment and Treatment Periods.

- A 1-day washout means that the particular medicine is not allowed during the calendar day before the Pretreatment Visit
- A 14-day washout means that the particular medicine is not allowed during the 14 calendar days before the Pretreatment Visit

1-Day Washout (no medicine during the calendar day before the Pretreatment Visit)

- 1. Any over-the-counter or prescription laxative, suppository, or enema (e.g., polyethylene glycol, lactulose, Fleet's) and any herbal or natural agent that a person might take for constipation. Note: The use of fiber, bulk laxatives, stool softeners (surfactants such as docusate), and probiotics is acceptable, provided the patient has been on a stable dose during the 30 days before the Screening Visit and plans to continue stable dosing throughout the trial.
- 2. Any medicine used to treat diarrhea (e.g., bismuth subsalicylate, kaolin)
- 3. NSAIDs if taken for abdominal pain or discomfort.
- 4. Others: Midazolam, Aluminum containing antacid.
- 14-Day Washout (no medicine during the 14 calendar days before the Pretreatment Visit)
- 1. Drugs with known pharmacological activity at 5-HT4, 5-HT2b or 5-HT3 receptors (e.g., cisapride, tegaserod, ondansetron, tropisetron, granisetron, dolasetron, and mirtazapine).
- 2. Any treatment specifically taken for IBS-C or CIC alone or in combination, including lubiprostone, an approved chloride channel activator that enhances intestinal fluid secretion, linaclotide, plecanatide, colchicine, and misoprostol. Note: patient has taken commercially available elobixibat, linaclotide or participated in a linaclotide or plecanatide or elobixibat clinical study during the 30 days before the Screening Visit.

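### The SBM, the unit of the primary endpoint, is defined inconsistently, and no definition exempts the bulk laxatives that the protocol permits

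*Protocol*

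**What the plan says.** **The definitions.** The synopsis, under the primary endpoint, says: "SBM is defined as the bowel movement occurring in the absence of laxative use or manual disimpaction in last 24 hours". Section 6.3.1 repeats this almost word for word: "SBM is defined as bowel movement occurring in the absence of laxative use or manual disimpaction in last 24 hours". The synopsis gives the same 24-hour rule again under time to first SBM.

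The footnote to the endpoint list in section 4.3.1 differs. It requires the "absence of laxative, suppository, or enema use 24 hour of the BM or the calendar day before the BM", and it does not mention manual disimpaction.

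Section 6.3.2, under time to first SBM, says: "SBM is defined as a bowel movement that occurred in the absence of a laxative use or manual disimpaction". No window follows.

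**The rescue rule.** Section 5.4 says that a movement "will not be recorded in the analysis of efficacy if it occurs within 24 hour after the last administration of a rescue medication". The synopsis has the same rule.

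**The permission.** Exclusion criterion 21 in section 5.2 notes: "The use of fiber, bulk laxatives, or stool softeners [such as docusate] was acceptable provided the patient had been on a stable dose", with the intention to continue through the trial. Section 8.4 says that "the use of fiber, bulk laxatives, stool softeners [surfactants such as docusate], and probiotics are acceptable" on the same condition. Inclusion criterion 5, by contrast, asks patients to give up any laxative in favour of rescue medicine and carves out nothing.

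**The concern.** The SBM count decides who is randomized (fewer than 3 per week in the pretreatment period), sets the baseline, and is the primary endpoint. CSBM response, SBM within 24 hours of the first dose and time to first SBM all derive from it. Weekly stool consistency, straining, bloating and discomfort are averaged over SBMs only. If the rule is not fixed, one diary can give different eligibility decisions and different endpoint values, and nothing in the protocol says which rule governs.

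The missing exemption is a separate problem. The protocol itself calls bulk laxatives laxatives and allows them throughout. Every SBM definition disqualifies a movement after laxative use without saying that permitted use is different. Taken at its word, the rule cancels the movements of a patient who is complying fully with the protocol.

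**Working it through.** The protocol gives no figure for this point, so the first check is a comparison of the texts.

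| Place | Window | What disqualifies a movement | Permitted agents exempt? |
|---|---|---|---|
| Synopsis (primary endpoint; time to first SBM) and 6.3.1 | 24 h | laxative, manual disimpaction | not stated |
| 4.3.1 footnote | 24 h or previous calendar day | laxative, suppository, enema | not stated |
| 6.3.2 (time to first SBM) | none given | laxative, manual disimpaction | not stated |
| Synopsis and 5.4 (rescue counting rule) | 24 h | rescue medicine | not applicable |

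**Window.** Take a dose t hours after midnight. The synopsis rule blocks the next 24 h. The 4.3.1 rule blocks until the end of the following calendar day, which is 48 - t hours: between 24 and 48 h, with a mean of 48 - 12 = 36 h if t is uniform over the day.

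**A patient on a permitted daily bulk laxative, read literally.**
- Under 4.3.1, the calendar day before any movement always contains a dose, so no movement counts.
- Under the 24-hour rule with dosing at a fixed time, no movement falls more than 24 h after the last dose, so the count is 0. In a simulation with dose times varying by ±2 h, about 2.7% of movements qualified.
- Baseline is then about 0, which is below 3 per week, so the entry rule is met by construction. The on-treatment count is about 0, so the change is about 0 in either arm.
- A CSBM must first be an SBM, so the patient cannot respond. The four weekly symptom scores become 0/0.
- Under the rescue counting rule alone, the same patient's movements would count unless they fell within 24 h of rescue.

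**Power, for illustration only.** Inputs from section 13.2: significance level 2.5% (sidedness not stated there), power 95%, 60 completers per arm, about 20% dropout. The inflation reproduces: 120/(1 - 0.20) = 150. The 60 per arm cannot be reproduced, because no effect size or SD is given. The standardized effect is therefore back-solved as d = (z_alpha + z_0.95) × √(2/60):
- one-sided 2.5%: (1.960 + 1.645) × 0.1826 = 0.658
- two-sided 2.5%: (2.241 + 1.645) × 0.1826 = 0.710

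Let a share f of each arm have change exactly 0. The others have SD 1, with mean m on placebo and m + d on elobixibat. Then:
- mean difference = (1 - f)d
- placebo variance = (1 - f)(1 + m²) - [(1 - f)m]²; the same formula with m + d gives the active arm
- power = Φ(difference / √[(sum of variances)/60] - z_alpha)

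Example with f = 0.10, m = 0.5, one-sided. The difference is 0.9 × 0.658 = 0.592. The variances are 0.9 × 1.25 - 0.45² = 0.9225 and 0.9 × (1 + 1.158²) - 1.042² = 1.021. The standard error is √(1.9435/60) = 0.180, and 0.592/0.180 - 1.960 = 1.33, so power is 0.908.

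| Assumed share f | One-sided, m = 0.5 | One-sided, m = 1 | Two-sided, m = 0.5 | Two-sided, m = 1 |
|---|---|---|---|---|
| 0 | 95% | 95% | 95% | 95% |
| 5% | 93.1% | 91.9% | 92.9% | 91.5% |
| 10% | 90.8% | 88.1% | 90.3% | 87.1% |
| 20% | 85.0% | 78.5% | 83.4% | 75.9% |

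**The case against.** Much can be said for the protocol.

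- **The primary definition is stable where it matters most.** The synopsis and 6.3.1 agree. This stands: the real conflict on the window is with the 4.3.1 footnote. But that footnote sits directly under the list of efficacy endpoints, and nothing ranks it below the others.
- **A reader might infer that three competing windows are in force.** The documents do not support that. The untimed wording in 6.3.2 has a synopsis counterpart, for the same endpoint, that carries the 24 hours. It is evidently a dropped phrase.
- **A reader might infer wide disagreement about agents.** Exclusion criterion 3 already treats suppositories and enemas as forms of laxative intake. The rescue rule is a counting rule consistent with the 24-hour definition, because bisacodyl is a laxative. Exclusion criterion 14 removes patients who commonly use digital manoeuvres, so leaving disimpaction out of 4.3.1 will rarely matter.
- **A reader might infer that any patient on a permitted agent can never have an SBM.** That is too strong. The text says stable dose, not daily. Under the 24-hour rule the count is exactly zero only if doses are no more than 24 h apart. Fibre and stool softeners are listed beside bulk laxatives and are not clearly called laxatives.
- **The authors probably meant non-permitted laxatives**, since section 8.4 places the permission inside the laxative prohibition. That is likely, but no definition says so. Section 2 describes the earlier Japanese trial's SBM by reference to rescue medication, so a narrower wording was at hand, and the primary endpoint does not use it. Inclusion criterion 5 pulls the other way.

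Nor can this be left to the analysis plan: sites apply the SBM count at the randomization visit, and the texts contradict each other rather than omit a detail.

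**Conclusion.** The point holds on two counts. First, 4.3.1 conflicts with the synopsis and 6.3.1: a dose blocks 24 to 48 h under one text and 24 h under the other, disimpaction counts in one and not in the other, and 6.3.2 has lost its window. Second, permitted bulk laxatives are not exempt in any SBM definition. Read literally, a daily user has essentially no SBMs, passes the entry threshold automatically, contributes a change of about zero and has undefined SBM-averaged scores.

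The size is not known. The ranges of 92-93%, 87-91% and 76-85% power rest on a back-solved effect size, assumed shares of 5%, 10% and 20%, an assumed placebo change of 0.5 to 1 SD, a comparison of mean changes, and sites applying the literal reading.

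Two further inferences are not supported:
- That the calendar-day clause raises blocked diary time from 33% to 50% (24/72 against 36/72). This assumes rescue every 72 h, whereas the 72 hours run from the last bowel movement. The two rules differ only for a movement 24 to 48 h after a dose, and such a movement moves the next 72-hour trigger to at least 96 h after that dose. That gives at most 24/96 = 25% against 36/96 = 37.5%, unless rescue is taken for intolerable symptoms. Blocked time is also not the share of movements lost.
- That the clause favours elobixibat because placebo patients use more rescue. The protocol gives no rescue rates by arm.

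**What to change.** Write one SBM definition and use it in the synopsis, 4.3.1, 6.3.1 and 6.3.2, for eligibility, baseline and every SBM-based endpoint. It should:

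- keep the 24-hour window of the primary endpoint;
- list as disqualifying: rescue medicine; any other non-permitted laxative, suppository or enema; and manual disimpaction;
- state that the stable-dose agents permitted under exclusion criterion 21 and section 8.4 do not disqualify a movement.

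Reconcile the calendar-day clause in 4.3.1 with this definition and restore the window in 6.3.2. Inclusion criterion 5 must also be reconciled with exclusion criterion 21 and section 8.4. Which of them should give way is for the sponsor to decide.

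The cost is small: wording and one derivation rule. A 24-hour rule needs the diary to record the times of rescue use and of bowel movements. The diary form is not shown, and section 5.4 speaks only of daily rescue use. If only days are recorded, one stated day-based rule should be applied everywhere instead.
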